## 8.6 Reference population

As discussed in the introduction (section 1.2), in a prior study of neoadjuvant Sip-T, since the effect of systemic Sip-T administration on localized prostate cancer was unknown, a negative control was felt to be important to be confident that the observed changes in the study population were due to treatment effect. Therefore a group of 12 patients, who had undergone RP at UCSF without any neoadjuvant therapy, selected prior to undergoing any tissue analyses and matched to the study population using the UCSF CAPRA-S score for preoperative risk stratification were used as a negative control; these patients were selected from the surgical population at UCSF that provide separate, written consent to the use of their RP specimens for research purposes.

Similarly, in this study, a cohort of 12 patients not treated with any neoadjuvant therapy will be used as a negative control, since the effect of neoadjuvant PROSTVAC, ipilimumab, or the combination of PROSTVAC and ipilimumab in prostate cancer tissue is unknown. Patients will be selected from the RP population at UCSF who have provided separate, written consent to the use of their RP specimens for research purposes, and matched to the phase II study population using the UCSF CAPRA-S score for preoperative risk stratification. This analysis will provide confidence that the changes observed in the prostates of treated patients are due to neoadjuvant treatment effect. These 12 patients will not otherwise be included in the analyses as delineated in section 8.5.

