#### 3.1 Characteristics

This is a multicentered, open label, randomized phase II trial of PROSTVAC or ipilimumab or the combination of PROSTVAC and ipilimumab as neoadjuvant therapy in patients with localized PC. Eligible patients will be randomized to PROSTVAC monotherapy (Arm A), ipilimumab monotherapy (Arm B), or combination therapy with both PROSTVAC and ipilimumab (Arm C), prior to RP. In arm A, PROSTVAC- V will be administered subcutaneously as the primary vaccine on Day 1, which will be followed 2 weeks later with a series 2 PROSTVAC-F subcutaneous administrations, given 3 weeks apart (Day 15 and 36). In arm B, Ipilimumab will be administered twice, at a dose of 3 mg/kg, 3 weeks apart (Day 1 and 22). In arm C, PROSTVAC will be administered in the same schedule as given in arm A; Ipilimumab will be administered on the same days as PROSTVAC-F. In all three arms, RP will occur 21 days, or 3 weeks, following the final study treatment administration. No further study therapy will be administered following RP.

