### 3.3.1 Inclusion Criteria

For a subject to be eligible for participation in this study, *all* of the following criteria must be satisfied:

1. Patients must have histologically confirmed adenocarcinoma of the prostate without previous therapy for PC.
  - a. Treatment-naïve AND
  - b. Undergoing RP as initial, locally definitive therapy for PC AND
  - c. Eligible for RP in a 3 month timeframe AND
  - d. Able to consent for RP
2. Subject's archival prostate biopsy specimen is available, and subject consents to provide tissue for study endpoint analysis. The prostate biopsy slides or blocks must be available prior to starting any study treatment.
3. Age  $\geq$  18 years
4. Subject has an Eastern Cooperative Oncology Group (ECOG) performance status of 0 or 1 (Appendix 1).
5. Subject has adequate organ function, defined as:
  - a. White blood cell (WBC) count  $\geq$  3,000/mcL
  - b. Absolute neutrophil count (ANC)  $\geq$  1,500/mcL
  - c. Platelet count  $\geq$  100,000/mcL
  - d. Hemoglobin (Hgb)  $\geq$  10.0 g/dL
  - e. Creatinine  $\leq$  1.5x institutional ULN
  - f. Total bilirubin  $\leq$  1.5 x institutional ULN
  - g. Alanine aminotransferase (ALT)  $\leq$  1.5 x institutional ULN
  - h. Aspartate aminotransferase (AST)  $\leq$  1.5 x institutional ULN
6. No known history of human immunodeficiency virus (HIV) 1 and 2, human T-cell lymphotropic virus (HTLV)-I/II, and Hepatitis B and C.
7. Ability to understand a written informed consent document, and the willingness to sign it.
8. Because of the unknown potential risk to a gamete and/or developing embryo from these investigational therapies, subjects must agree to use adequate contraception (i.e. barrier method) for the duration of study participation, and for three months after discontinuing therapy.

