#### **6.1.4 Study Procedures: Radical Prostatectomy (ALL ARMS: 21 days following final dose of PROSTVAC and/or Ipi)**

- For Arms A&C, Day 57 +/- 7 days
- For Arm B, Day 43 +/- 7 days
- Radical prostatectomy will be performed by the treating urologic oncologist.
- Preoperative Physical exam

- Preoperative Vital signs including blood pressure, heart rate, respiratory rate, temperature, pulse oximetry
- Preoperative Medical history
- Immune monitoring (done preoperatively).
- Preoperative ECOG PS and IPSS.
- Preoperative labs,
  - CBC with differential and platelet count
  - Blood chemistry assessment, including: Alkaline phosphatase, ALT/AST, total bilirubin, calcium, phosphorus, BUN, creatinine, total protein, albumin, fasting glucose, potassium, sodium, chloride, LDH, carbon dioxide, lipase, amylase
  - TSH and T4
  - PSA
- Subjects will have a postoperative telephone follow-up assessment 10-42 days following RP as per the treating urologic and medical oncologists' discretion. At this time the following will be performed:
  - Concomitant medications
  - Evaluation of adverse events
  - Postoperative labs may be requested as per the treating urologic and medical oncologists' discretion
  -

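### Section 8.6 matches the reference men on CAPRA-S but not on biopsy-to-prostatectomy interval, so elapsed time cannot be separated from drug effect in the treated-versus-reference comparison

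*Combined protocol and SAP*

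**What the plan says.** Section 8.6 states that "a cohort of 12 patients not treated with any neoadjuvant therapy will be used as a negative control". On their source it says "Patients will be selected from the RP population at UCSF", and on selection that they are "matched to the phase II study population using the UCSF CAPRA-S score for preoperative risk stratification". No criterion is given for the time from biopsy to RP.

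The section then gives the cohort its purpose: "This analysis will provide confidence that the changes observed in the prostates of treated patients are due to neoadjuvant treatment effect". It adds that "These 12 patients will not otherwise be included in the analyses as delineated in section 8.5". The synopsis (Study Design) also says that each arm, and the arms combined, will be compared with this reference group.

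The outcome is a before/after measure. Section 7.1.1 defines it as the RP-to-biopsy ratio of CD3+ cells per unit area, and 8.5.1 calls a rise of at least 2-fold a positive response. Inclusion criterion 2 in 3.3.1 fixes the baseline tissue: "Subject's archival prostate biopsy specimen is available, and subject consents to provide tissue for study endpoint analysis". It sets no maximum age for that specimen.

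Section 6.1.4 times the surgery: "For Arms A&C, Day 57 +/- 7 days", and Day 43 with the same window for Arm B.

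**The concern.** All three randomised arms are active. The reference men are therefore the trial's only evidence of how the biopsy-to-RP ratio behaves without study drug. A control for a before/after ratio does that job only if its before/after gap resembles the gap in the treated men. Matching on a cancer risk score does not secure this.

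In treated men, several weeks of protocol therapy are built into the gap. Reference men go to surgery on whatever timetable applied to them, and 8.6 neither sets nor records it. If CD3+ density changes with time after a needle biopsy, for any reason other than drug, the two groups could differ in the primary measure while the drugs do nothing. They could equally look alike while the drugs work. What is at stake is the statement in 8.6 that the reference analysis supports attribution to treatment.

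**Working it through.** **1. Time that treatment adds before surgery.** Days from Day 1 to RP = study day of RP minus 1, using the windows in 6.1.4.

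- Arms A and C: Day 57 ± 7 is Day 50 to Day 64, so 49 to 63 days (7 to 9 weeks).
- Arm B: Day 43 ± 7 is Day 36 to Day 50, so 35 to 49 days (5 to 7 weeks).

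Total gap between specimens = (biopsy to Day 1) + (Day 1 to RP). The plan sets no upper limit on the first term. For reference men neither a minimum nor a maximum is given for the total. The synopsis (Duration of Therapy) instead puts RP 12 weeks, or 84 days, after the start of therapy. That lies outside both ranges, and the two places must be reconciled.

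**2. The plan's own precision figure.** Section 8.2 gives a 90% confidence interval of 6.6% to 49.5% with 13 men per arm. The exact (Clopper-Pearson) interval for 3/13 reproduces it. This figure concerns one treated arm and does not involve the reference men.

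**3. Can 12 reference men reveal the background rate by themselves?** With 0/12 responders, the exact two-sided 95% upper bound is 1 − 0.025^(1/12) = 26.5%. Even the most favourable reference result is compatible with an untreated responder rate far above 5%. Comparability has to come from how the men are selected.

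**4. Illustrative size in the treated-versus-reference contrast.** The documents give no estimate of drift, so every input here is an assumption:

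- the log2 ratio in untreated men is normal with median zero;
- 5% of untreated men reach a 2-fold rise, borrowing the threshold in 8.2, so SD = 1/1.645 = 0.608;
- treated men have a drift, not shared by the reference men, of 0.25 or 0.50 log2 units (1.19-fold or 1.41-fold);
- the drugs have no effect.

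Responder rate in treated men = 1 − Φ((1 − drift)/0.608):

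- drift 0.25: 1 − Φ(1.234) = 10.9%
- drift 0.50: 1 − Φ(0.822) = 20.5%

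Section 8.6 names no test or level for this contrast, so two are shown. The entries are the probability that 13 treated men are significantly higher than 12 reference men at 5%, summed over all binomial outcomes:

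| Treated rate | Fisher, two-sided 0.05 | z-test, two-sided 0.10 |
|---|---|---|
| 5% (no drift) | 0.02% | 1.3% |
| 10.9% | 0.5% | 9% |
| 20.5% | 6% | 32% |

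A drift in the opposite direction would hide a drug effect by the same mechanism.

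**The case against.** Four points can fairly be made for the plan.

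- **Direction.** Reference men also wait between biopsy and RP. Their wait could be shorter, equal or longer, and nothing in the documents says whether CD3+ density rises or falls over that time. A reader might infer that elapsed time will be counted as drug benefit. The documents do not support that; they support only that the two cannot be told apart. This objection stands.
- **Single-arm error.** A reader might set drift against a fixed 5% and note that the chance of at least 3/13 responders in an inactive arm rises from 2.5% to 16% or 52% under the same drifts. That calculation does not involve the reference men, so better matching would not change it. The plan has no 3/13 decision rule, and 8.2 describes 5% as a lower threshold, not as an observed untreated rate. The 13-versus-12 contrast is the relevant one, and its figures are much smaller.
- **Centre.** Section 3.1 says "This is a multicentered, open label, randomized phase II trial", while the reference men come from one centre. A reader might infer a site bias. A multiplicative site effect common to a man's two specimens cancels in the ratio. Only a difference between biopsy and RP handling that varies by site would remain, and the documents show none. This part does not carry the point.
- **Reach.** Section 8.5.1 compares combination with pooled monotherapy, and the arms pairwise, without the reference men. That is correct: how those men are chosen cannot affect these tests. The cohort is a supportive negative control that follows the earlier neoadjuvant sipuleucel-T study.

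What remains is that 8.6 asks this cohort to support attribution, and the one variable most directly tied to a before/after ratio is not among its matching criteria.

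**Conclusion.** The point holds in a limited form and is a cheap improvement. The interval between specimens is uncontrolled in the treated-versus-reference comparison, so a time-related change in CD3+ density is confounded with treatment there. That rests on the text of 8.6, 7.1.1, 3.3.1 and 6.1.4 and on day arithmetic, with no outside assumption.

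The size is not known. The error rates in the working rest on the assumed distribution, drifts and tests. They show that modest drift could matter under a liberal test and would matter little under a strict one. They are not an estimate of bias in this trial.

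**What to change.** In 8.6:

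- Record the biopsy-to-RP interval for every treated and every reference man.
- Select reference men before any tissue analysis, matching on that interval, within the range seen in treated men, as well as on CAPRA-S.
- Report the interval distribution in both groups beside the comparison.
- Where numbers allow, repeat the comparison in treated men from UCSF only, as a sensitivity check.

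Covariate adjustment for interval is not asked for. With 12 reference men and about 13 per arm it would be fragile, especially if the intervals barely overlap.

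The cost is a chart review for biopsy dates and a smaller pool of eligible reference men. Section 8.6 mentions consent for RP specimens only, so the sponsor should confirm that biopsy tissue and its date are available for the men chosen. No change to sample size, significance level or study procedures is needed. Matching after the tissue has been read would be post hoc, so the amendment should come first.

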## 8.7 Evaluation of Safety

Analyses will be performed for all patients having received at least one dose of study drug. The study will use the NCI CTCAE v4.03. In addition, safety data will be tabulated in aggregate and by treatment group within the safety population. The results will be tabulated for all toxicities observed. No statistical testing is planned for AE summaries.

# 9 Study Management

## 9.1 Pre-study Documentation

This study will be conducted in accordance with the ethical principles that have their origin in the Declaration of Helsinki as stated in 21 CFR §312.120(c)(4); consistent with GCP and all applicable regulatory requirements.

Before initiating this trial, the Investigator will have written and dated approval from the Institutional Review Board for the protocol, written informed consent form, subject recruitment materials, and

any other written information to be provided to subjects before any protocol related procedures are performed on any subjects.

The clinical investigation will not begin until either FDA has determined that the study under the Investigational Drug Application (IND) is allowed to proceed or the Investigator has received a letter from FDA stating that the study is exempt from IND requirements.

The Investigator must comply with the applicable regulations in Title 21 of the Code of Federal Regulations (21 CFR §50, §54, and §312), GCP/ICH guidelines, and all applicable regulatory requirements. The IRB must comply with the regulations in 21 CFR §56 and applicable regulatory requirements.

## **9.2 Institutional Review Board Approval**

The protocol, the proposed informed consent form, and all forms of participant information related to the study (e.g. advertisements used to recruit participants) will be reviewed and approved by the UCSF CHR (UCSF Institutional Review Board). Prior to obtaining CHR approval, the protocol must be approved by the Helen Diller Family Comprehensive Cancer Center Site Committee and by the Protocol Review Committee (PRC). The initial protocol and all protocol amendments must be approved by the IRB prior to implementation.

## **9.3 Informed Consent**

All participants must be provided a consent form describing the study with sufficient information for each participant to make an informed decision regarding their participation. Participants must sign the CHR-approved informed consent form prior to participation in any study specific procedure. The participant must receive a copy of the signed and dated consent document. The original signed copy of the consent document must be retained in the medical record or research file.

## **9.4 Changes in the Protocol**

Once the protocol has been approved by the UCSF CHR, any changes to the protocol must be documented in the form of an amendment. The amendment must be signed by the Investigator and approved by PRC and the CHR prior to implementation.

If it becomes necessary to alter the protocol to eliminate an immediate hazard to patients, an amendment may be implemented prior to CHR approval. In this circumstance, however, the Investigator must then notify the CHR in writing within five (5) working days after implementation. The Study Chair and the UCSF study team will be responsible for updating any participating sites.

## **9.5 Handling and Documentation of Clinical Supplies**

The UCSF Principal Investigator and each participating site will maintain complete records showing the receipt, dispensation, return, or other disposition of all investigational drugs. The date, quantity and batch or code number of the drug, and the identification of patients to whom study drug has been dispensed by patient number and initials will be included. The sponsor-investigator will maintain written records of any disposition of the study drug.

The Principal Investigator shall not make the investigational drug available to any individuals other than to qualified study patients. Furthermore, the Principal Investigator will not allow the investigational drug to be used in any manner other than that specified in this protocol.

## 9.6 Case Report Forms (CRFs)

The Principal Investigator and/or his/her designee, will prepare and maintain adequate and accurate participant case histories with observations and data pertinent to the study. Study specific electronic Case Report Forms (eCRFs) will document safety and treatment outcomes for safety monitoring and data analysis. All study data will be entered into OnCore® via standardized eCRFs in accordance with the CTMS study calendar, using single data entry with a secure access account. The Clinical Research Coordinator (CRC) will complete the eCRFs as soon as possible upon completion of the study visit; the Investigator will review and approve the completed eCRFs.

The information collected on eCRFs shall be identical to that appearing in original source documents. Source documents will be found in the patient's medical records maintained by UCSF personnel. All source documentation should be kept in separate research folders for each patient.

In accordance with federal regulations, the Investigator is responsible for the accuracy and authenticity of all clinical and laboratory data entered onto eCRFs. The PI will approve all completed eCRFs to attest that the information contained on the eCRFs is true and accurate.

All source documentation and CTMS data will be available for review/monitoring by the UCSF DSMC and regulatory agencies.

The Principal Investigator will be responsible for ensuring the accurate capture of study data. At study completion, when the eCRFs have been declared to be complete and accurate, the database will be locked. Any changes to the data entered into the eCRFs after that time can only be made by joint written agreement among the Study Chair, the Trial Statistician, and the Protocol Project Manager.

Each participating site will complete study specific eCRFs for safety monitoring and data analysis. Each site will enter the study data into OnCore® via standardized eCRFs in accordance with the CTMS study calendar, using single data entry with a secure access account. The participating site's Clinical Research Coordinator (CRC) will complete the eCRFs; the Investigator will review and approve the completed eCRFs – this process must be completed within 5 business days of the visit. Study data from the participating site will be reported and reviewed in aggregate with data from patients enrolled at the coordinating center, UCSF. All source documentation and CTMS data will be available for review/monitoring as needed.

## 9.7 Registration/Enrollment

Screening procedures will occur when a subject and investigator signs and dates an informed consent form and the subject provides authorization to use protected health information. The informed consent form will be completed prior to any study-specific procedures. Screening procedures that are standard of care and were performed prior to consent, do not need to be repeated if they were conducted within the eligible screening period, unless otherwise specified.

To initiate enrollment, the investigator will verify eligibility according to all inclusion and exclusion criteria and complete the Enrollment Form. All eligible subjects must be centrally registered through the UCSF GU Clinical Research Office. To complete the registration process, the study site must fax or email the signed completed study-specific eligibility checklist, registration form, all source documents verifying eligibility, any supporting documents, and the signed informed consent. These data must also be entered into the OnCore database. Once the enrollment information is received at UCSF, the Study Chair will review the packet and if eligibility is confirmed, he will sign the registration form and assignment to treatment can occur. UCSF will provide the participating site with the signed registration approval. Subjects failing to

meet all study eligibility requirements will not be registered. See Section 3.6 for randomization details.

## **9.8 Oversight and Monitoring Plan**

The UCSF Helen Diller Family Comprehensive Cancer Center DSMC will be the monitoring entity for this study. The UCSF DSMC will monitor the study in accordance with the NCI-approved Data and Safety Monitoring Plan (DSMP). The DSMC will routinely review all adverse events and suspected adverse reactions considered “serious”. The DSMC will audit study-related activities to ensure that the study is conducted in accordance with the protocol, local standard operating procedures, FDA regulations, and Good Clinical Practice (GCP). Significant results of the DSMC audit will be communicated to the IRB and the appropriate regulatory authorities at the time of continuing review, or in an expedited fashion, as applicable. See Appendix 2 Data and Safety Monitoring Plan for a Phase 2 or 3 Institutional Study, for additional information.

# **10 Protection of Human Subjects**

## **10.1 Protection from Unnecessary Harm**

Each clinical site is responsible for protecting all subjects involved in human experimentation. This is accomplished through the CHR mechanism and the process of informed consent. The CHR reviews all proposed studies involving human experimentation and ensures that the subject's rights and welfare are protected and that the potential benefits and/or the importance of the knowledge to be gained outweigh the risks to the individual. The CHR also reviews the informed consent document associated with each study in order to ensure that the consent document accurately and clearly communicates the nature of the research to be done and its associated risks and benefits.

## **10.2 Protection of Privacy**

Patients will be informed of the extent to which their confidential health information generated from this study may be used for research purposes. Following this discussion, they will be asked to sign the HIPAA form and informed consent documents. The original signed document will become part of the patient's medical records, and each patient will receive a copy of the signed document. The use and disclosure of protected health information will be limited to the individuals described in the informed consent document.

